## **5.7 Subject Replacement Strategy**

A subject that discontinues from the trial will not be replaced.

## **5.8 Beginning and End of the Trial**

Each subject is considered to be enrolled when the subject (or the subject’s legal representative) has provided written informed consent in accordance with local requirements.

This long-term trial will start with enrollment of the first subject who completes the initial 104-week trial and chooses to participate in the long term trial. This trial will end after 5 years after the first subject enrolls (260 weeks), or a) when the drug either becomes commercially available (locally), or b) when the MK-8931 program is terminated (whichever comes first). Duration of participation may also be limited based on local regulations. Each subject is considered to have ended participation in the trial when he/she has completed the last protocol-specified contact (e.g., visits or telephone contacts) or has prematurely discontinued from the trial. A subject will be considered a completer of this long-term trial if he/she is still continuing in the trial when the trial is stopped.

A subject is considered to have discontinued after he/she has withdrawn consent or has been discontinued under the conditions specified in Section 7.1.4.1. Given the exploratory nature of the long-term trial, the retrieved dropout approach employed in the initial 104-week trial will be discontinued from this trial. All applicable activities scheduled for the final trial visit should be performed at the time of treatment discontinuation as defined in the long-term trial Flow Chart in Section 6.0.

A subject is considered to have been lost to follow-up if he/she is unable to be contacted by the investigator. The end of participation for a subject lost to follow-up is the last known contact (e.g., visit or telephone contact).

### **5.9 Clinical Criteria for Early Trial Termination**

This trial may be terminated early by eDMC for safety concerns or based on the results of the interim efficacy analysis for futility of the initial 104-week trial (See section 8.1.4).

The clinical trial may be terminated early if the extent (incidence and/or severity) of emerging effects/clinical endpoints is such that the risk/benefit ratio to the trial population as a whole is unacceptable. In addition, further recruitment in the trial or at a particular trial site(s) may be stopped due to insufficient compliance with the protocol, GCP and/or other applicable regulatory requirements, procedure-related problems or the number of discontinuations for administrative reasons is too high.

## 6.0 TRIAL FLOW CHART

**NOTE: Subject participation in the long term trial (Part II) is optional and will only be conducted where approved by local authorities.**

Extension Trial Period:	Treatment																	
Visit Number (counting from the initial 104-week trial; Part I)	12B b	TC d	13	TC d	14	15	16	17	18	19	20	21	22	23	24	TC f	UV	ETV
Scheduled Week a (based on date of randomization in initial 104-week trial; Part I)	104	106	108	112	117	130	156	182	208	234	260	286	312	338	364			
Visit Window (Weeks)		±1	±1	±1	±1	±4	±4	±4	±4	±4	±4	±4	±4	±4	±4			
Administrative Procedures																		
Informed Consent	X																	
Collect Subject Identification Card															X			
Inclusion/Exclusion Criteria	X																	
Record Concomitant Medication	X	X	X	X	X	X	X	X	X	X	X	X	X	X	X		X e	X
Clinical Procedures/ Assessments																		
Vital Signs c			X		X	X	X	X	X	X	X	X		X	X		X e	X
Body Weight			X		X	X	X		X		X				X		X e	X
Directed Physical & Neurological Examinations							X		X		X		X		X		X e	X
Directed Skin Examination by Site Physician						X	X		X		X		X		X		X e	X
12-Lead Electrocardiogram			X														X e	
CDR						X	X		X		X		X		X			X
ADAS-Cog (13-item)					X	X	X		X		X		X		X			X
Cognition Battery																		
COWAT					X	X	X		X		X		X		X			X
Trial Making Test (A & B)					X	X	X		X		X		X		X			X
CERAD Verbal Fluency					X	X	X		X		X		X		X			X
Digit Span Test					X	X	X		X		X		X		X			X
Digit Symbol-Coding (DSC)					X	X	X		X		X		X		X			X
ADCS-ADLMCI																		
ADCS-ADL MCI					X	X	X		X		X		X		X			X
MMSE						X	X		X		X		X		X			X
C-SSRS: Since Last Visit			X		X	X	X	X	X	X	X	X	X	X	X		X e	X
NPI						X	X		X		X		X		X			X

Extension Trial Period:	Treatment																		
Visit Number (counting from the initial 104-week trial; Part I)	12B b	TC d	13	TC d	14	15	16	17	18	19	20	21	22	23	24	TC f	UV	ETV	
Scheduled Week a (based on date of randomization in initial 104-week trial; Part I)	104	106	108	112	117	130	156	182	208	234	260	286	312	338	364				
Visit Window (Weeks)		±1	±1	±1	±1	±4	±4	±4	±4	±4	±4	±4	±4	±4	±4				
Modified RUD Lite: Follow-Up						X	X		X		X		X		X			X	
HEA						X	X		X		X		X		X			X	
EQ-5D						X	X		X		X		X		X			X	
CAM	X-----To be completed only for adverse events of delirium-----																		
Structural MRI																		X e	
Monitor for Progression to Dementia h	X		X		X	X	X	X	X	X	X	X	X	X	X		X	X	
Adverse Event Monitoring	X	X	X	X	X	X	X	X	X	X	X	X	X	X	X	X	X	X	
Laboratory Procedures/ Assessments																			
Hematology and Chemistry Blood Samples c			X		X	X	X		X		X		X		X			X e	X
Urinalysis c			X		X	X	X		X		X		X		X			X e	X
Trial Medication Procedures																			
Dispense Trial Medication	X		X		X	X	X	X	X	X	X	X	X	X	X			X g	
Medication Compliance		X	X	X	X	X	X	X	X	X	X	X	X	X	X			X	X
Drug Accountability Assessment			X		X	X	X	X	X	X	X	X	X	X	X			X	X

Extension Trial Period:	Treatment																	
Visit Number (counting from the initial 104-week trial; Part I)	12B b	TC d	13	TC d	14	15	16	17	18	19	20	21	22	23	24	TC f	UV	ETV
Scheduled Week a (based on date of randomization in initial 104-week trial; Part I)	104	106	108	112	117	130	156	182	208	234	260	286	312	338	364			
Visit Window (Weeks)		±1	±1	±1	±1	±4	±4	±4	±4	±4	±4	±4	±4	±4	±4			

ADAS-Cog = Alzheimer’s Disease Assessment Scale Cognitive subscale (modified: 13-item with delayed memory recall and number cancellation tasks); ADCS-ADLMCI= Alzheimer’s Disease Cooperative Study Activities of Daily Living (MCI Version); AE = Adverse Event; CAM = Confusion Assessment Method; CDR = Clinical Dementia Rating; COWAT = Controlled Oral Word Association Test; C-SSRS = Columbia Suicide Severity Rating Scale; DSC = Digit Symbol-Coding; EQ-5D = EuroQoL Five Dimension Questionnaire; ETV = Early Termination Visit; HEA = Health Economic Assessment; MCI = Mild Cognitive Impairment; MMSE = Mini-Mental State Examination; MRI = magnetic resonance imaging; NPI = Neuropsychiatric Inventory; RUD Lite Resource Utilization in Dementia Lite Questionnaire; TC = telephone call; UV = Unscheduled Visit

a. Visits scheduled during the long term trial (Part II) will be based off of the date of randomization in the initial 104-week trial (Part I). The timing of each visit is relative to Study Day 1 of that subject with Study Day 1 defined as the date of randomization into the initial 104-week trial (which should also be the date of the first administration of trial medication in the initial 104-week trial). However, if a subject enters the extension trial at a different time point than visit 12, i.e. V12 and V12B occur on different days, subsequent visits should be based on the date V12B actually occurred and not the date of randomization.

b. Visit 12 from Part I and Visit 12B from Part II are considered a single visit and can be conducted on the same day. Subjects with a gap in therapy of > 4weeks may be allowed to continue if reason for the delay was due to, for example, HA/IRB approval, etc. If there is a gap in study therapy >3 months the sponsor should be consulted. It is recognized that lab results will not be available at Visit 12/12B if they occur on the same day. Therefore, such subjects may be enrolled prior to receiving these results; upon their receipt, if the PI feels they are clinically unacceptable the subject should be discontinued.

c. Vital Signs and laboratory samples should be collected for subjects with > 3 month gap in therapy between visit 12 and 12B.

d. Telephone contact with subject and trial partner/caregiver by site to assess safety, AEs, concomitant medications, medication compliance, and any other issues. Any telephone contact may be conducted as an in-person unscheduled visit if the subject or caregiver expresses a preference for this or of the site has significant safety/tolerability concerns.

e. Procedures may be performed if clinically indicated as determined by the investigator.

f. Telephone contact will be performed to assess for adverse events that may have occurred up to 14 days (+ 1-week) following cessation of study medication.

g. Drug dispensing may be performed at unscheduled visits at the discretion of the Investigator.

h. Progression to dementia should be evaluated at all visits during the long term trial until the investigator or qualified designee considers the subject as having progressed to dementia (AD or non-AD). Cases of progression in this trial will not be reviewed by an adjudication committee; therefore the final decision on progression will be the opinion of the investigator or qualified designee. Note: Subjects who were confirmed to have progressed to AD dementia by the adjudication committee in the initial 104-week trial may not continue in this trial. For those subjects for whom the adjudication committee rendered a decision of non-AD dementia, the subject may continue in this trial if in the investigator’s opinion the subject did not progress to AD or non-AD dementia during the initial 104-week trial.

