### **7.1.2.2.4 Skin Examinations**

To monitor for hypopigmentation, skin examinations will be performed by a site physician at the visits specified in Section 6.0, Trial Flow Chart. At Weeks 130, 156, 208, 260, 312, and 364, a site physician will perform a directed examination of the subject's skin. In addition, sites will instruct subjects to perform a self-examination of their skin between clinic visits (with the assistance of their trial partner, if needed). Subjects should report any abnormal loss of skin pigment to the site. The site physician's examination will focus on exposed skin and any areas of pigment loss noted by the subject or trial partner. If a clinically significant area of hypopigmentation is observed, the site should refer the subject to a dermatologist or medical expert for further follow-up. At each scheduled assessment, the following information should be recorded: whether significant sites of skin hypo- or depigmentation were observed, and any adverse events.

Based on the local standard of care, the investigator should refer subjects to a dermatologist or medical expert if: 1) a clinically significant area of skin develops hypopigmentation compared to baseline\*; or 2) if needed based on their clinical judgment. The following criteria are provided to guide the investigator but are not meant to be inclusive or to require referral in all cases.

- 1) A clinically significant area of hypopigmentation may include:
  - a) those greater than 3x3 cm
  - b) a smaller area (e.g., 1x1 cm) on the face or hands
  - c) a speckled pattern involving a larger amount of body surface area or
  - d) a smaller area (e.g., 1x1 cm) of complete pigment loss.

**Hypopigmentation for criterion 1** is defined as a decrease in skin color relative to the surrounding skin and its prior baseline appearance.

2) Clinical judgment criteria include:

- a) In the investigator's judgment, the hypopigmentation requires evaluation by an expert (e.g., small lesions on the face), or
- b) The subject or caregiver is distressed by the appearance of the skin lesion or hypo/depigmentation.

Dermatologists will evaluate and treat any lesions based on local standard of care. No special procedures are required per protocol.

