### **8.2.8 Statistical Methods for Safety Analyses**

Subjects from all three arms (40 mg / 40 mg, 12 mg / 12 mg, Pbo / 40 mg) will be included in the safety analyses. Where applicable, treatment comparisons will be conducted between the 40 mg / 40 mg and Pbo / 40 mg arms, as well as between the 12 mg / 12 mg and Pbo / 40 mg arms.

Safety and tolerability will be assessed by clinical review of all relevant parameters including AEs, laboratory tests, vital signs, and ECG measurements. The primary approach for all safety analyses will be an On Drug approach, i.e., one that includes only those observations obtained from the first dose through 14 days after the last dose of study medication. A supportive approach will include all post-treatment observations, including those observations obtained more than 14 days after the last dose of study medication.

The analysis of safety results will follow a tiered approach (Table 7). The tiers differ with respect to the analyses that will be performed. Safety parameters or adverse experiences of special interest that are identified a priori constitute “Tier 1” safety endpoints that will be subject to inferential testing for statistical significance with p-values and 95% confidence intervals provided for between-group comparisons. Other safety parameters will be

considered Tier 2 or Tier 3. Tier 2 parameters will be assessed via point estimates with 95% confidence intervals provided for between-group comparisons; only point estimates by treatment group are provided for Tier 3 safety parameters.

Adverse experiences (specific terms as well as system organ class terms) and predefined limits of change in laboratory, vital signs, and ECG parameters (see Section 12.3) that are not pre-specified as Tier-1 endpoints will be classified as belonging to "Tier 2" or "Tier 3", based on the number of events observed. Membership in Tier 2 requires that at least 1% of the subjects in any treatment group exhibit the event; all other adverse experiences and predefined limits of change will belong to Tier 3.

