**12.2 Approximate Blood/Tissue Volumes Drawn/Collected by Trial Visit and by Sample Types**

Trial Visit (continuing from the initial 104-week trial; Part I)	Visit 13	Visit 14	Visit 15	Visit 16	Visit 18	Visit 20	Visit 22	Visit 24
Scheduled Week (based on date of randomization in initial 104-week trial; Part I)	108	117	130	156	208	260	312	364
Blood Parameter	Approximate Blood Volume (mL)							
Hematology	2	2	2	2	2	2	2	2
Serum/Plasma Chemistry	5	5	5	5	5	5	5	5
Expected Total (mL)	7	7	7	7	7	7	7	7

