### 12.3 Predefined Limits of Change Criteria

Table 1

Predefined Limits of Change Criteria for Laboratory Data

Laboratory Test	Criteria † as a % of a Limit of Normal Range
Hematology	
Hematocrit (M)	≤94.9% LLN
Hematocrit (F)	≤94.1% LLN
Hemoglobin (M)	≤90.5% LLN
Hemoglobin (F)	≤81.9% LLN
WBC	≤64.2% LLN ≥149.0% ULN
Neutrophils	≤37.0% LLN
Eosinophils	≥147.0% ULN
Platelets	≤57.7% LLN ≥177.7% ULN
Hepatic Function	
Bilirubin	≥166.7% ULN
Alkaline Phosphatase	≥300% ULN
SGOT	≥300% ULN
SGPT	≥300% ULN
Renal Function	
Creatinine	≥142.9% ULN
Clinical Chemistry	
Sodium	≤94.7% LLN ≥105.4% ULN
Potassium	≤88.2% LLN ≥111.1% ULN
† A laboratory value must represent a worsening from baseline (i.e., be more abnormal in the direction of interest) to meet the definition. LLN=Lower limit of normal. ULN=Upper limit of normal.	

Table 2

Predefined Limits of Change Criteria for Vital Signs,  
Weight, and Temperature

Measurement	Criteria
Systolic blood pressure	$\geq 180$ mm Hg and $\geq 20$ mm Hg increase from baseline
	$\leq 90$ mm Hg and $\geq 20$ mm Hg decrease from baseline
Diastolic blood pressure	$\geq 105$ mm Hg and $\geq 15$ mm Hg increase from baseline
	$\leq 50$ mm Hg and $\geq 15$ mm Hg decrease from baseline
Pulse	$\geq 120$ bpm and $\geq 15$ bpm increase from baseline
	$\leq 50$ bpm and $\geq 15$ bpm decrease from baseline
Weight	$\geq 7\%$ increase from baseline
	$\geq 7\%$ decrease from baseline
Temperature	$\geq 101^\circ\text{F}$ and $\geq 2^\circ\text{F}$ increase from baseline ( $\geq 38.3^\circ\text{C}$ and $\geq 1^\circ\text{C}$ increase from baseline)
Respiratory rate	$> 25$ or increase of $\geq 10$ (per minute) from baseline
	$< 5$ or decrease of $\geq 10$ (per minute) from baseline

Table 3

Predefined Limits of Change Criteria for ECGs

Measurement	Criteria
QTc Interval Fridericia	Prolongation compared to baseline $\geq 30$ to $\leq 60$ msec
	Prolongation compared to baseline $> 60$ msec
	Value $\geq 500$ msec

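### The flow chart leaves vital signs and body weight unmarked at Visit 22 (Week 312), a full clinic visit, so one late scheduled safety measurement is lost without explanation

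*Combined protocol and SAP*

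**What the plan says.** Section 6.0 gives vital signs as "Vital Signs c X X X X X X X X X X X X e X" and body weight as "Body Weight X X X X X X X X e X". These quotes close up the empty cells, so the positions have to be read in the chart itself. Vital signs have eleven scheduled marks, one at every clinic visit from 13 to 24 except Visit 22. Body weight has seven, at every visit with laboratory samples except Visit 22.

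Other parts of the protocol treat Week 312 as a full visit:
- Section 7.1.2.2.4: "At Weeks 130, 156, 208, 260, 312, and 364, a site physician will perform a directed examination".
- Section 12.2, on blood draws: "Scheduled Week (based on date of randomization in initial 104-week trial; Part I) 108 117 130 156 208 260 312 364".

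Sections 7.1.2.2.1 and 7.1.2.2.2 describe how vital signs and weight are taken but give no visits and no exception. Footnote c, the only footnote on the vital signs label, concerns a treatment gap between Visits 12 and 12B.

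Three provisions set the size of the loss. Section 5.8 ends the trial 260 weeks after the first subject enrolls. It also says of the last measurement: "All applicable activities scheduled for the final trial visit should be performed at the time of treatment discontinuation". Section 8.2.8 defines the main safety approach as "one that includes only those observations obtained from the first dose through 14 days after the last dose of study medication".

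**The concern.** Long-term safety is the first primary objective (Section 3.1). Section 12.3, in the table headed "Predefined Limits of Change Criteria for Vital Signs", sets limits for blood pressure, pulse, weight (a change of 7% or more), temperature and respiratory rate. Section 8.2.8 analyses these as on-drug incidences, so each missing scheduled value is one fewer chance to record an event.

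The blanks do not look deliberate. Visits 21 and 23, on either side, are lighter and do have vital signs. Sections 2.1, 7.1 and 7.1.5 make the chart the governing schedule. The only scheduled ECG in the extension is at Week 108, so pulse and blood pressure are the only routine cardiovascular measurements after that. In the subjects with the longest exposure, a transient late change could be missed and a sustained one would be found later.

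**Working it through.** The plan gives no figure of its own on this point. The check is a reading of the chart followed by interval arithmetic.

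**1. Scheduled weeks in Section 6.0**

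| Row | Weeks marked | Week 312 |
|---|---|---|
| Vital signs | 108, 117, 130, 156, 182, 208, 234, 260, 286, 338, 364 | blank |
| C-SSRS | 108, 117, 130, 156, 182, 208, 234, 260, 286, 312, 338, 364 | marked |
| Body weight | 108, 117, 130, 156, 208, 260, 364 | blank |
| Hematology and chemistry | 108, 117, 130, 156, 208, 260, 312, 364 | marked |
| Physical and neurological exam | 156, 208, 260, 312, 364 | marked |
| Skin exam, CDR | 130, 156, 208, 260, 312, 364 | marked |

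The vital signs and weight rows each have 18 cells for 18 visit columns, so the blank is not a shifted column. The skin row matches Section 7.1.2.2.4 and the laboratory row matches Section 12.2. Vital signs differ from C-SSRS, and weight from the laboratory row, only at Week 312.

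**2. Scheduled intervals**
- Weight: 364 − 260 = 104 weeks, against 52 with Visit 22 marked.
- Vital signs: 338 − 286 = 52 weeks, against 26.

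**3. Who can reach these visits**

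Visit 22 falls 312 − 104 = 208 weeks into the extension, or 204 with the 4-week window. A subject must therefore enter within 260 − 204 = 56 weeks of the first entrant. For Visit 24 the limit is 260 − (260 − 4) = 4 weeks. Entry is assumed uniform over 104 weeks (range 52 to 156), with no dropout:
- Visit 22: 56/104 = 54% (100% to 56/156 = 36%).
- Visit 24: 4/104 = 3.8% (4/52 = 7.7% to 4/156 = 2.6%).

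Dropout lowers these shares. Section 8.2.11.1.2 assumes 25% dropout by Week 104, 37% by Week 130, and 90% of completers continuing. Retention over the first 26 extension weeks is then 0.63/(0.75 × 0.90) = 93.3%. If that rate held (assumed), 0.933^8 ≈ 58% would remain at 208 weeks, and the share reaching Visit 22 would be 0.54 × 0.58 ≈ 31% (21% to 58%).

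**4. Longest interval from Week 260 on**

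Assume extension follow-up is uniform on 208 to 260 weeks, so treatment stops between Weeks 312 and 364, with a final measurement at that point. Let L be the weeks from Week 260 to treatment stop, uniform on 52 to 104.
- Weight as written: L, with mean (52 + 104)/2 = 78. With Visit 22 marked: 52.
- Vital signs as written: stopping by Week 338 gives 26 to 52 weeks (mean 39), and stopping later gives 52. The mean is (39 + 52)/2 = 45.5. With Visit 22 marked: 26.

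**5. Delay to the first weight after a sustained change**

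Onset is uniform between Week 260 and treatment stop.
- As written: mean of L/2 = 39 weeks.
- With Visit 22 marked: mean of [52 × 26 + (L − 52)²/2]/L = (2704 ln 2 + 2028 − 2704)/52 = 23.0 weeks.

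**6. Transient change of d weeks coinciding with a planned weight**
- As written: mean of d/L = d × (ln 2)/52.
- With Visit 22 marked: mean of [d + min(d, L − 52)]/L.

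| d (assumed) | As written | Visit 22 marked |
|---|---|---|
| 13 weeks | 17.3% | 31.8% |
| 26 weeks | 34.6% | 58.5% |
| 52 weeks | 69.3% | 100% |

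**The case against.** A mark lost when the PDF table is converted to text would leave just such an empty cell, and the correct cell count does not exclude that. The cross-checks confirm other rows, not these two. In the converted chart the hematology/chemistry and urinalysis rows also carry a surplus cell. That surplus, however, lies at the unscheduled and early-termination end of a later part of the table, and the scheduled weeks there agree with Section 12.2. Losing a mark at the same column in two adjacent rows is unlikely, though not impossible.

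The stronger argument is that little is lost. These limits of change are Tier 2 or Tier 3, without p-values, and Section 8.2.8 calls the confidence intervals descriptive. Adverse events, laboratory tests and a directed examination are still recorded at Visit 22, and Section 7.1 and footnote e allow vital signs or weight when clinically indicated. The full 104-week interval needs a subject who reaches Visit 24, and dropout shrinks the group reaching Visit 22. Even with the cell marked, a 13-week change is caught only about a third of the time.

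All of this limits the size of the point and none of it removes it. Measurement on clinical suspicion does not replace routine measurement. Because so few subjects reach Visit 24, the next planned weight after Week 260 is, for most who reach Visit 22, the one at treatment stop.

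**Conclusion.** The concern holds. Two routine safety measurements are missing from a full clinic visit, with no reason given, in the schedule that sites follow. The loss is one intermediate late value per measure in each subject who reaches Week 312. The end-of-treatment value survives and falls inside the on-drug window. Subjects who stop before Week 312 are unaffected. All arms share one schedule, so no between-arm bias is shown, and the Week 130 CDR-SB analysis is not touched.

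The scheduled intervals come straight from the chart. The average intervals, delays and detection shares also depend on the assumed uniform follow-up and onset and on the assumed durations of change. The share reaching Visit 22 depends on the assumed entry pattern. The 54% ignores dropout and is an upper bound for entry over 104 weeks.

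**What to change.** Mark vital signs and body weight at Visit 22 (Week 312) in the Section 6.0 flow chart, in line with the other rows of that column. Scheduled vital signs then stay at 26-week intervals from Week 130 to Week 364 (12 measurements instead of 11), and weight at 52-week intervals from Week 156 (8 instead of 7). If the blanks are intended, a footnote should say so and why. The cost is two table cells and a few minutes at a visit already held, with no new visit, equipment or staff.
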